10.1.2 Rates of new episode of fever during neutropenia

We will also perform an analysis of the rate of a new episode of fever during neutropenia, among afebrile children. We will compare the rates between the same three treatment group as for the analysis of the rates of SAE presented in Section 10.1.1, using the same methodology.

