4.1 Primary objective, endpoint and estimand

The two treatment strategies (interventions) being investigated are the following.

- **Experimental (“short”):** discontinuation of antibiotics, despite neutrophil count $< 0.5 \times 10^9$ cells/L, after 48 hours of apyrexia and clinical stability. A child is considered clinically stable by the treating physician when there is resolution of all symptoms and signs of infection, and normalization of vital signs including heart rate, respiratory rate, oxygen saturation, blood pressure, and daily diuresis.
- **Control (“standard” or “long”):** discontinuation of antibiotics when either i) neutrophil count is $\geq 0.5 \times 10^9$ cells/L, and the child is afebrile and clinical stable or ii) the child has received 10 days of antibiotics and has been afebrile and clinically stable for 7 days.

The two treatment strategies are followed from randomization until neutrophil recovery (i.e. neutrophil count $\geq 0.5 \times 10^9$) or 28 days, whichever comes last. In case of relapsing fever, the patients continue to be treated according to the same treatment strategy (“short” or “long”). Randomization could occur from 36 hours after initiation of antibiotics until 48 hours of apyrexia and clinical stability (when the two treatment strategies can start to differ).

The primary outcome is the number of days without antibiotic treatment within the first 28 days after treatment initiation. For each of the 28 days, the information of whether the patient received antibiotics has been collected. The typical reasons for restarting antibiotics are new onset of fever, typically:

- febrile neutropenia (without documented infection)
- fever with or without neutropenia due to a possible or proven bacterial infection, including bacteremia (bacterial infection in the blood stream), pneumonia, skin infection, gastroenteritis or typhilitis (infection in the gut), urinary infection or other types of focal infections; side effects to chemotherapy that is accompanied by fever, such as pancreatitis

Restarting antibiotics might also happen without new onset of fever, for instance in case of suspicion of infection (e.g. focal symptoms from skin, lungs, gastrointestinal, etc).

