5.7.3 Fever and episode of fever

Fever is pivotal to define **S2** and **S3**. We say that a child has fever when the child fulfills (at least) one of these two conditions: a) a single temperature $\geq 38.5^\circ \text{C}$ once or b) temperature $\geq 38.0^\circ \text{C}$ sustained within one hour. An episode of fever starts as soon as we observed condition

a) or b). That is, as soon as a single temperature ≥ 38.5 is observed or once we have observed a temperature ≥ 38.0 for one hour (whichever comes first). An episode of fever stops 48 hours after the last time we observe the child with fever. That is, 48 hours after the last time a temperature ≥ 38.5 is observed or 48 hours after the last we have observed a temperature ≥ 38.0 for one hour, whichever comes last. Accordingly, a new episode of fever cannot start before 48 hours after the last time we observed condition a) or b). The temperature was monitored very regularly (≥ 1 per day) as is standard in this population of children with cancer.

To define **S3** (Days alive without fever within 28 days), we sum the duration of all episodes of fever within 28 days. A fever duration is computed as the time difference between two dates and times: that of fever stop² and that of treatment start. Hence, fever durations expressed in days are not whole numbers, but decimal numbers.

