10.1 Additional outcome analyses

10.1.1 Rates of SAE during neutropenia

We will compute the rate of SAE during neutropenia, within 28 days from treatment initiation, among children that are:

- (i) currently treated with antibiotics
- (ii) not currently treated with antibiotics.
- (iii) not currently treated with antibiotics, but have stopped antibiotic treatment less than three days ago.

For the primary analysis of these rates, we will pool the data of the two arms. The rationale for pooling the data is that antibiotic treatment are expected to have a short term effect. Hence, it seems reasonable to assume that a child currently treated with antibiotics is approximately similarly protected no matter how long ago the treatment has started, either many days ago (as typical in

the “long” arm) or just a few days ago (as typical in the “short” arm). We will compare the rates via rate ratios. The rate ratio of main interest is that comparing the rates of the first and third groups. Indeed, an interesting research question is: *“Is there an increased risk of SAE just after stopping the antibiotic treatment during neutropenia?”* (here “just after stopping” is defined as “within three days from stopping”). Comparing the rates of the first and second groups is also of interest.

To compute the rates, we will divide the number of events by the total time duration (days) at risk, as commonly done. Note that by definition of the rate of interests (during neutropenia), a time period (day) is not “at risk” if ANC is not $< 0.5 \times 10^9$ cells/L. Time at risk will be expressed in days, but computed as detailed in Section 5.7.2. This means that a continuous time scale will be used, not a discrete one. Exact Poisson inference will be used to compute 95% CI for the rates and the rate ratios using the `poisson.test()` function of R. Specifically, we will look at the rate of the first SAE. Although SAEs is a potentially recurrent event, we will investigate the rate of the first of possibly several SAEs. Descriptive statistics about children experiencing more than one SAE (if any) will be provided for completeness. We will consider presenting a descriptive plot similar to that of Figure 1 to transparently report the raw data about numbers of events and days at risk and show how these analyses summarize these raw data.

For completeness, we will also redo the analyses stratified per arm (i.e., without pooling the data).

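### SAP 10.1.2 does not exclude the 48 hours after the last fever from time at risk, although no new episode can occur then; counting them biases the rate ratios against stopping antibiotics

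*SAP*

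**What the plan says.** Section 10.1.2 of the SAP defines the analysis in two sentences. The risk set is given by: "We will also perform an analysis of the rate of a new episode of fever during neutropenia, among afebrile children". The comparison is between the three treatment groups of Section 10.1.1, "using the same methodology". Those groups are (i) on antibiotics, (ii) off antibiotics, and (iii) off antibiotics for less than three days. Section 10.1.1 pools the arms, names (iii) against (i) as the main contrast, uses continuous time to the first event, and spells out one exclusion from time at risk: time when the ANC is not below 0.5. It adds: "For completeness, we will also redo the analyses stratified per arm (i.e., without pooling the data".

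Section 5.7.3 holds two notions of fever:

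- A state: "We say that a child has fever when the child fulfills (at least) one of these two conditions", both being temperature criteria.
- An episode: "An episode of fever stops 48 hours after the last time we observe the child with fever". It follows that "a new episode of fever cannot start before 48 hours after the last time we observed condition a) or b". For S3, "we sum the duration of all episodes of fever within 28 days".

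Section 4.1 has the short arm stop "after 48 hours of apyrexia and clinical stability". A long-arm child who is still neutropenic stops only after 10 days of antibiotics and 7 afebrile, stable days.

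**The concern.** The event counted in 10.1.2 is a new fever episode. By 5.7.3 its rate is zero in the 48 hours after the last fever, whatever the treatment. The time-at-risk rule taken over from 10.1.1 was written for severe adverse events, which have no such blackout, and nothing in 10.1.2 adapts it.

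The window does not fall evenly across the groups. Under both stopping rules a child who is still neutropenic is on antibiotics throughout it, so it goes almost entirely into group (i). Groups (ii) and (iii) begin at or after its end. Counting the window therefore lowers only the on-antibiotic rate. The analysis addresses whether fever returns just after antibiotics are stopped, and it could show an excess that the definition of an episode has created.

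**Working it through.** **1. Is the window in the risk set?** Section 10.1.2 does not say. Two readings are available:

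- *Afebrile means not currently having fever.* This matches the definition of having fever in 5.7.3. It also matches the stopping rules in 4.1 (repeated in 10.2.3), where 48 hours of apyrexia and 7 afebrile days are counted as time free of raised temperature. The window is included.
- *Afebrile means outside a fever episode.* This is how S3 treats fever time, since it sums whole episodes including their last 48 hours. The window is excluded.

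The first is the SAP's usual sense of the word. The second has to be borrowed from another outcome.

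**2. Closed form for the size if the window is included.** The SAP gives no rate or person-time for this analysis, so there is no figure to reproduce. From the SAP: the window is 2 days and randomization is 1:1. Assumed: *S* and *L* are the mean on-antibiotic, afebrile (temperature sense), neutropenic days per episode in the short and long arm; every child is still neutropenic through the window; the hazard *h* of a new episode is the same on and off antibiotics.

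- Group (i) rate = h(S + L − 4)/(S + L)
- Off-antibiotic rate = h
- Off/on ratio = (S + L)/(S + L − 4), where the true value is 1

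| S | L | Share of group (i) time with no possible event | Off/on ratio |
|---|---|---|---|
| 2 | 7 | 4/9 = 44% | 9/5 = 1.80 |
| 3 | 8 | 4/11 = 36% | 11/7 = 1.57 |
| 2 | 4 | 4/6 = 67% | 6/2 = 3.00 |
| 3 | 5 | 4/8 = 50% | 8/4 = 2.00 |

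L of 7 to 8 describes children who stay neutropenic until the 7-day afebrile rule lets them stop. L of 4 to 5 describes earlier neutrophil recovery.

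**3. Simulation with no true effect.** Assumed: hazard 0.03 or 0.06 per day from 48 hours after the last fever; mean remaining neutropenia 5, 10 or 15 days (exponential, capped at 24); long arm stops at 7 or 8 afebrile days; short arm stops at 48 hours or up to 12 hours later; follow-up ends at the first new episode or at neutrophil recovery; 200,000 episodes per setting.

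| Pooled ratio | Window included | Window excluded |
|---|---|---|
| (iii)/(i) | 1.90 to 2.76 | 0.97 to 1.03 |
| (ii)/(i) | 1.90 to 2.75 | 0.98 to 1.02 |

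These values exceed 1.57 to 1.80 because some long-arm children recover before day 7, which shortens eligible on-antibiotic time. A separate simulation (mean last fever day 3, mean ANC recovery day 13, hazard 0.02 to 0.04) gave 1.86 to 1.93 with the window and 0.99 to 1.01 without it.

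**4. Per-arm repeat, short arm.** If every child stops exactly at 48 hours, first-course on-antibiotic afebrile time is all window and the simulated ratio is infinite. With stopping up to 12 hours later it is 9.5 to 11.9, still with no true effect.

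**5. What remains after exclusion.** The long arm's share of eligible group (i) time is (L − 2)/(S + L − 4). With S = 2 it is 100%. With S = 2.5 and L = 7 it is 5/5.5 = 91%. With S = 3 and L = 8 it is 6/7 = 86%.

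**The case against.** The strongest reply is that 10.1.2 nowhere says the 48 hours count. Its event is an episode, and 5.7.3 defines when an episode ends. S3 treats those hours as fever, and 10.1.1 drops time that the definition of the rate rules out. A careful analyst could apply the same logic and exclude the window, in which case no bias arises.

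That stands as far as it goes: a reader might infer that the plan prescribes the biased denominator, and the text does not support so firm a statement. But the excluding reading depends on carrying over S3's convention, which 5.7.3 gives for S3 and not for this analysis. The SAP's own use of fever and afebrile points the other way, and the only exclusion written out is the ANC one. Two analysts following the document could obtain ratios that differ by a factor of about two.

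A reader might also infer that short-arm on-antibiotic afebrile time consists entirely of the window, so that its rate must be zero. The documents do not support this either. Stopping also requires clinical stability, which may come later than apyrexia. Section 10.2.3 expects deviations of under 24 hours for logistical reasons. Late-positive cultures lead to targeted treatment, antibiotics may be restarted without fever, and group (i) is not limited to first courses. *Most* is supported; *all* is not.

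**Conclusion.** The point holds as a risk set that is not properly fixed. Section 10.1.2 fails to exclude a 48-hour window in which its own event cannot occur, and on the SAP's usual sense of afebrile that window enters the denominator of group (i). The direction of the bias follows from 5.7.3 and the stopping rules in 4.1: it runs against stopping antibiotics.

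The size, roughly 1.6 to 3 times, rests on assumed neutropenia durations and stopping times, and in the simulations on assumed hazards; none of these is in the SAP. It is about 1.0 if the window is excluded. Under either reading the short arm has little or no valid on-antibiotic time in the first course, and the plan does not acknowledge this for the per-arm repeat.

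A reader might infer that the trial's main comparison is affected. It is not: this is one of the other analyses in Section 10, and Section 5.3 limits formal testing to the primary estimand. The change should still be made, because the contrast bears on safety just after stopping and will be reported with an exact interval.

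**What to change.** State in 10.1.2 that time at risk for a new fever episode starts when the previous episode has ended under 5.7.3, that is, 48 hours after the last observed fever, and that neither events nor days before that point are counted. Apply this to all three groups, pooled and per arm.

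Report eligible time by group and arm, and say that group (i) then comes almost wholly from the long arm when short-arm children stop close to 48 hours. Report the short-arm on-antibiotic rate and ratio as not estimable if little or no eligible time remains.

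The cost is a sentence or two in the SAP and one line in the derivation of time at risk. The downside is less on-antibiotic time and so a wider interval. No data collection or patient management changes.

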10.1.3 Cumulative incidence plots

To describe the timing of the binary secondary outcome **S1** and **S2**, we will report the cumulative incidence/risk function per arm graphically and with pointwise 95% CIs. That is, we will present the proportion of events observed before day t , for $t = 0, 1, 3, \dots, 28$, for each arm. The CIs will be computed again using GEE. A similar approach will be used for **S4**, if relevant (i.e., if several deaths are observed).

Cumulative incidence functions per arm will also be reported for the time to bone marrow recovery (**S5**). However, the method to compute them will be that accounting for interval censoring outlined in Section 8.2.

10.1.4 Subgroup analyses

There is only one pre-specified subgroup analysis.

- episodes with ANC at presentation $\leq 0.1 \times 10^9$ cells/L, i.e., episodes of patients considered at “very high” risk.

We will replicate the main analysis of the primary outcome described in Section 7, up to minor differences for the baseline covariate adjustment. Specifically, for any baseline categorical variable, a group of less than five episodes will be combined with the smallest group of more than five episodes. Similarly, we will also drop knots if the subgroups that they implicitly define do not

all contain at least than five episodes (0-5, 6-12 and ≥ 13 years for age and 0-49, 50-99, ≥ 100 for thrombocyte, in 10^9 cells/L unit). We will also replicate the analysis of main analyses of the secondary outcomes described in Section 8.

10.2 Descriptive analyses

10.2.1 Recruitment

Recruitment of the patients and episodes will be summarized via descriptive statistics. Especially, start and end dates of recruitment will be presented as well as a flowchart, inspired by the CONSORT guidelines and template [22]. Number of patients, number of episodes and the distribution of number of episodes per patient will be provided.

10.2.2 Baseline characteristics

Baseline characteristics will be descriptively summarized per arm, using the “All episodes analysis set”. The list of baseline variables to be summarized includes:

- Sex (male/female)
- Age (year)
- Study site
- Year of inclusion (Nov 2020 to Dec 2021, 2022, 2023 or 2024)
- Cancer disease and treatment cycle (ALL induction, ALL not induction, AML, Relapsing ALL, Lymphoma, Neuroblastoma, Other)
- Days from cancer diagnosis to randomization
- Empirical antibiotic treatment at randomization
- ANC at presentation
- Minimum ANC within the time interval ranging from presentation to randomization
- Thrombocyte count at presentation
- Neutropenia duration at randomization

For quantitative variables, we will present median, first and third quartiles and also minimum and maximum. Categorical variables will be summarized by counts and percentages. The number and proportions of missing values, if any, will be reported for each variable, per arm. Hypothesis tests will not be performed to compare baseline characteristics, but clinical importance of any imbalance will be noted. This is in line with usual recommendations [21].

10.2.3 Adherence

For each arm, we will document the number of patients who did not receive the “short” or “long” treatment strategy to which they were randomized. Specifically, we will report the number and proportion of:

- patients randomized to “short” who continued antibiotics longer than they should according to the “short” duration treatment strategy.
- patients randomized to “long” who stopped antibiotics before they should according to the “long” duration treatment strategy.

The reasons for that will be provided too, as these data have been collected. Note that the relevant data have been collected to identify such patients. Especially, information about the time at which the treatment should have stopped has been collected. That is, the time corresponding to:

- 48h of apyrexia and stability (for patients in the “short” arm)
- either i) neutrophil count is $\geq 0.5 \times 10^9$ cells/L, and the child is afebrile and clinical stable or ii) the child has received 10 days of antibiotics and have been afebrile and clinically stable for 7 days (for patients in the “long” arm).

Daily data about antibiotic treatment have been collected too. Hence, it is possible to check that the random assignment to “long” or “short” is consistent with the daily data about antibiotics and the time at which the treatment should be discontinued. Any inconsistency of more than 24h will be reported, but any data “inconsistency” of less than 24h will not be considered as an inconsistency. This is because such small inconsistencies are expected because of logistical constraints. For instance, small inconsistencies might happen for patients treated with out-patient intravenous antibiotics by portable infusion pumps according to local guidelines. These patients need to come back to the hospital regularly for filling of pumps. For example, a patient needs to come back to the hospital to have the pump that administers antibiotics removed (hence continuing the treatment slightly longer than planned). A patient expected to fulfill the criteria to stop antibiotics within less than 24h might also not receive a new pump (hence stopping slightly earlier than planned).

10.2.4 Type of severe adverse events

To complement the analysis of **S1** (any severe adverse event), we will present the number and proportion of each individual component of the composite outcome **S1**, per arm. The individual component are listed in Section 4.2 to define **S1**. The type of observed severe focal infections will also be listed (e.g., lungs, abdomen, skin).

10.2.5 Descriptive statistics of outcomes

Outcomes (primary, secondary and exploratory) will also be descriptively summarized, per arm, using the “All episodes analysis set”. Similar descriptive statistics as for baseline characteristics will be used. Mean and standard deviation will be presented instead of median, first and third quartiles (or in addition to those) whenever appropriate. The number and proportions of missing data will be reported if any, but we do not expect any.

10.2.6 Dotplots and boxplots of the primary outcome

The raw data of the primary outcome will be presented graphically via dotplots (one per arm). Boxplots will be overlaid, to summarize the raw data in each group graphically.

10.2.7 Descriptive plot of antibiotics, neutropenia and more

For each of the 28 first days of each patients, a plot will show the days:

- with and without antibiotics
- with or without neutrophil count $< 0.5 \times 10^9$ cells/L

An example of such a plot is Figure 1. We will consider enriching the plot by additionally showing the days with and without fever and the occurrences of SAEs. The main results of the trial will essentially be numerical summaries of this exhaustive graphical representation, which should provide the “full picture”.

[figure not shown]

Figure 1: Example of descriptive plot to show the days with antibiotics (in blue when randomized to “long” duration; red when randomized to “short”) and neutropenia (grey) for each patient, within the 28 days follow-up. The plot shows the data for 5 hypothetical patients in each arm. Total number of days with antibiotics per patients are shown in the right margin (in color), together with the number of days with neutropenia (in grey). Note that treatment and neutropenia can start and stop at any time of the day and these times have been recorded (as shown in the plot). Hence the durations in days in the right margin are not whole numbers.

10.2.8 Regularity of neutrophil count measurements

Secondary outcome **S5** (Time to bone marrow recovery) is interval censored as it is observed from repeated measures of neutrophil counts (see Section 5.4). Descriptive statistics about the regularity of the data collection will be presented per arm, to document how interval censoring impacts the analysis of the secondary outcome **S5**.

10.2.9 Blood culture turning positive after randomization

Inclusion criteria include the fact that the blood culture (or other clinically relevant culture) was not positive after 48h (i.e., “negative”). Very few culture are expected to become positive after 48h (< 5%). Hence, we expect that the culture of very few randomized episodes will become positive. For completeness, we will report the number and proportion per arm. Descriptive statistics about the time at which the culture becoming positive will also be described.

11 Sample size determination and power calculations

11.1 Sample size determination

For the number of episodes to include in the trial, the initial sample size calculation was performed as followed. A mean number of 16 empirical antibiotic therapy free days was expected in the experimental group, versus 13 days in the control group. A standard deviation of 6.5 days in each arm was expected. These expected values were, among other things, based on previous results from a similar study in adult patients [1]. Standard sample size calculation for 1:1 randomization [3, Sec. 3.2.1] suggested that

$$n/2 = \frac{2 \times 6.5^2 \times (1.96 + 1.282)^2}{(16 - 13)^2} \approx 99$$

in each group, hence $n = 198$ in total, would be sufficient to obtain 90% power to show a significant difference in mean between the two arms, while controlling the type-I error at 5% (using a usual two-sided test). Accounting for up to 10% of drop-outs, the sample size was increased to $n = 198/(1 - 0.1) = 220$.

